Experience with recruitment and retention of adults with CUD: [name] (primary mentor), has completed multiple NIH-funded studies involving individuals with CUD. Of immediate relevance to the proposed project, the candidate recently completed a 4-session human laboratory pilot study in non-treatment seeking adults with CUD. Over the course of approximately 8 months, a total of 61 patients were consented, of which, 49 were randomized, 39 (80%) completed all 4 study sessions, and 33 (67%) completed through follow-up. These studies demonstrate the ability to effectively recruit and retain individuals with CUD for brief interventions.

Experience with adjunctive treatments for psychosocial interventions: Developing adjunctive treatments for CUD has been a career research focus of primary mentor [name]. Most recently, she completed a pilot study on oxytocin-enhanced MET for cannabis dependence²⁶. Participants who received MET plus oxytocin demonstrated reductions in amount (grams) used daily ($p=0.012$) and number of cannabis sessions per day ($p=0.003$), while those who received MET plus placebo did not. In addition to [name] experience, off-site mentor [name] also has considerable expertise integrating psychosocial interventions with novel adjunctive treatment approaches (see *Biosketch*).

Experience with the ABM paradigm: The candidate recently completed a randomized sham-controlled pilot study investigating the effect of ABM in non-treatment seeking adults with CUD (N=33). Results showed a trend of blunted cannabis cue-induced craving at end of treatment among ABM participants compared to controls ($p=0.051$) (see Figure 1), and preliminary evidence of gender modification of cannabis outcomes; men receiving ABM reported fewer sessions per day at the end of treatment (EOT) compared to women ($p=0.022$), while there was no gender

difference in the sham-control group (Figure 2). These pilot findings suggest that ABM may be efficacious in reducing cue-reactivity and improving cannabis outcomes, and that gender may

Figure 1: Cannabis craving by group and visit adjusted for baseline.

[figure not shown]
[figure not shown]

Figure 2: Cannabis use by gender and condition at EOT.

moderate this effect. As proposed in this K23 application, further investigation into the feasibility and efficacy of ABM as a potential adjunct to psychosocial treatments is warranted.

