containing 250 chips that are assigned a certain value. Two-hundred thirty chips denote a small amount (\$1.00), 18 chips denote a moderate amount (\$10.00), one chip denotes a large amount (\$50.00), and one chip denotes a jumbo amount (\$100.00). Participants will be allowed three draws at the screening visit if they provide a UDS and five draws at subsequent visits if their saliva drug screens are negative. Participants will be paid with a Greenphire ClinCard.

Total possible reimbursement is \$295/participant plus the sum of what is gathered from the chip pick.

[figure not shown]
D4.i. Confidentiality: Confidentiality of all research data will be maintained by keeping all data in a locked file, limiting access to the computer database to only study personnel, and by using patient code numbers/initials as opposed to names on all paperwork. Any requests for the release of patient information will be referred to the candidate.

D4.i. Study Timeline

	Screen	BL/ Wk1	Wk 2	Wk 3	Wk 4	1 Month FU	6 Month FU
MINI	x						
DSM-5 CUD criteria		x			x	x	x
Urine pregnancy test	x	x			x		
Urine cannabinoid test, TLFB, CWS, PSQI, Menstrual History, HAM-A, HAM-D	x	x	x	x	x	x	x
MJ Summary Sheet, Self-reports	x	x			x	x	x
Neuropsych testing, Digit Span, SDMT		x			x	x	
Approach Bias assessment, Cue reactivity			x		x	x	
Integrated Treatment (MET/CBT + ABM)*		x	x	x	x		

*Participants will receive three sessions of MET/CBT over the four weeks.

D4.j. Study visit flow chart

D5. Statistical Considerations.

General Analysis: Baseline clinical and demographic characteristics will be collected and contrasts performed between treatment groups. Continuous and ordinal characteristics will be compared using a Wilcoxon Rank-Sum test while categorical characteristics will be compared using a Pearson Chi-Square test. In addition to baseline treatment group differences, preliminary analysis of baseline characteristics will examine significant correlates of outcomes. Characteristics found to be significantly associated with the primary outcome measures, will be included as covariates in the initial stages of adjusted model development. All analyses will be performed on the intent-to-treat sample consisting of all randomized subjects.

Study Aims: Aim 1 is to evaluate the efficacy of ABM in the reduction of cannabis cue reactivity outcomes between BL and EOT/FU, as well as the variance around each estimate. Generalized linear mixed (GLM) effects regression

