models will be used to estimate each parameter and variance estimate of ABM or sham-ABM on cue reactivity measured at EOT and FU visit. Model based means and associated standard errors will be used to assess treatment group differences at EOT and FU. These methods are particularly well suited in instances where missing data is present. Aim 2 is to evaluate the efficacy of ABM on the reduction of cannabis use characteristics between BL and EOT/FU, as well as the variance around each estimate. Cannabis use data will be collected using the TLFB (proportion of use days, abstinence) and creatinine-adjusted cannabinoid levels (CN-THCCOOH) and will be compared between treatment groups using GLM models with appropriate distributional assumptions. Study data will be modeled as time invariant summary measures of the use at the end of the 4-week study period. Secondarily, we will also assess the efficacy of ABM on abstinence at FU (four-week abstinence). Study abstinence will be determined using UDS results (≤ 50 ng/ml) in concert with daily self-reported use. Exploratory Aim 1 will investigate the influence of gender on the treatment outcome and parameter estimates. Model interaction terms between study treatment assignment and gender will be added to each model developed for study aims 1 and 2 and tested for evidence of effect modification. When gender modification is present, pairwise comparisons within and across groups will be examined to assess the direction and magnitude of the modification. Additional analysis will assess neuropsychological data between groups over time using GLM models with appropriate distributions. Relative improvements over time associated with ABM will be assessed using between group comparisons taken at EOT and FU visits while controlling for baseline response data. Continuous outcome data will be assessed using a Gaussian distribution and count data will be assessed using a Poisson distribution. Second, neuropsychological data will be incorporated in the primary outcome models using interactions with treatment assignment to assess possible moderating effects on reported cannabis craving and use. Lastly, when ABM shows a significant relationship with changes in cannabis craving and use, neuropsychological measures will be assessed for mediating effects on the significant outcomes using bootstrap methods⁴⁵. All analyses will be conducted using SAS v. 9.4.

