Statistical Power and Sample Size: The proposed study is largely focused on obtaining preliminary data to inform and power a larger randomized controlled trial to assess ABM for CUD. However, the proposed sample size will allow for adequate power to assess the primary study aims. Primary AIM 1: Evaluate the efficacy of ABM combined with MET/CBT on cue-reactivity in adults with CUD. In a previous pilot study, we found evidence of greater reductions in cue induced cannabis craving at the end of treatment in those receiving active ABM as compared to sham ABM (MCQ: 43.2 ± 1.0 vs. 39.5 ± 1.0 , $\Delta = 3.7 \pm 1.4$, $d = 0.58$). We assume that the effect will be similar in the proposed study; however, we will measure use during the final treatment visit as well as at the FU visit. Under a correlated measures model assumption with a conservative within subjects correlation of $\rho = 0.8$, a sample size of 84 participants would be necessary to detect the noted treatment effect size with 80% power and a type 1 error rate of 5%. To account for an expected attrition of 20% based on our pilot study we have inflated our sample size to **106 participants (n=53 in each treatment assignment)**. To achieve a randomized sample of 106 participants, we will need to enroll one hundred and thirty-six (136) participants. With a randomized sample of 106 participants, our 80% confidence interval around the sample estimated variance will be within 18% of the true population variance and the conservative upper estimate of the variance will be used to inform the power of the larger R01. Primary AIM 2: Evaluate the efficacy of ABM combined with MET/CBT on cannabis outcomes in adults with CUD. Cannabis use will be measured by a combination of self-reported use days and (CN-THCCOOH) levels measured following the 4th week of treatment. The sample size of 53 randomized participants (42 completers) in each treatment group necessary to provide adequate power in Aim 1 will provide 80% power with a type 1 error rate of 5% to detect a similar effect size to Aim 2 ($d = 0.58$) in EOT (CN-THCCOOH) levels between study groups under similar model assumptions. The sample size of 42 completers per group will provide 80% power with a type 1 error rate of 5% to detect an 18% decrease in the proportion of use days in the ABM (39%) as compared to Sham (57%). Thus, a **total randomized sample size of n=106** participants will provide adequate power to address the clinically meaningful study aims in a statistically efficient manner.

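### The 80% power stated for end-of-treatment CN-THCCOOH uses Aim 1's two-visit variance; one value per person gives about 75%

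*Combined protocol and SAP*

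**What the plan says.** All of this is in D5 of the combined protocol and SAP.

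- **Aim 1 power (Statistical Power and Sample Size).** The effect is d = 0.58, taken from pilot craving scores at end of treatment. The text adds that "we will measure use during the final treatment visit as well as at the FU visit", assumes a within-subject correlation of 0.8, and arrives at 84 participants for 80% power at 5% type 1 error. With 20% attrition this becomes 106 randomized, 53 per arm.
- **Aim 2 power (same paragraph).** The 42 completers per arm are said to give 80% power for d = 0.58 "in EOT (CN-THCCOOH) levels between study groups under similar model assumptions". The outcome is described as "levels measured following the 4th week of treatment".
- **Aim 2 model (Study Aims).** "Study data will be modeled as time invariant summary measures of the use at the end of the 4-week study period". Follow-up enters Aim 2 as a secondary analysis of abstinence. The sentence that introduces the aim is wider: "Aim 2 is to evaluate the efficacy of ABM on the reduction of cannabis use characteristics between BL and EOT/FU".
- **Covariates (General Analysis).** Baseline characteristics found to be significantly associated with the primary outcomes "will be included as covariates in the initial stages of adjusted model development".

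**The concern.** The Aim 1 sample size gains precision from averaging two correlated visits. The Aim 2 statement keeps the same number per arm, effect size and power, but for an outcome that the plan describes as one value per person at end of treatment. A single value cannot have the variance of a two-visit mean, so the same 42 per arm cannot give the same power.

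CN-THCCOOH is one of the primary outcomes listed in D1 and is part of Hypothesis 2. D5 uses this statement to conclude that 106 randomized participants are enough for the study aims. If the single-value reading is right, the chance of missing a true d of 0.58 is about one in four rather than the stated one in five.

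**Working it through.** **Inputs, all from D5:** d = 0.58; type 1 error 5%, taken as two-sided (the plan does not say); power 80%; correlation between visits 0.8; 42 completers per arm; 20% attrition.

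**1. Reproduce the plan's 84.** For one measure per person:

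n per arm = 2 × (1.960 + 0.842)² / 0.58² = 46.66.

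The variance of the mean of two measures correlated at 0.8 is (1 + 0.8)/2 = 0.90 times that of one measure:

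n per arm = 46.66 × 0.90 = 42.00, so 84 in total.

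Normal-approximation power at 42 per arm is then 80.0%. Attrition: 84/0.8 = 105, or 106 for equal arms. Both of the plan's figures are matched.

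The plan shows no formula, so the two-visit mean is an inference. The other designs tried do not return 84:

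| Design | Total N for 80% power |
|---|---|
| Two-visit mean, two-sided | **84** |
| One measure, two-sided | 94 |
| Two-visit mean, one-sided | 68 |
| One measure, one-sided | 74 |
| One measure, baseline-adjusted at 0.8 | 34 |
| Change score at 0.8 | 38 |
| Two-visit mean, baseline-adjusted | 26 |

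**2. Power for one end-of-treatment value, 42 per arm, d = 0.58.**

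Normal approximation: 0.58 × √(42/2) = 2.658, and 2.658 − 1.960 = 0.698, which gives 75.7%.

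Noncentral t with 82 degrees of freedom: 74.8%.

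| Method | Two-visit factor | One value | Loss |
|---|---|---|---|
| Normal | 80.0% | 75.7% | 4.3 points |
| t | 79.1% | 74.8% | 4.3 points |

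**3. What 80% would need with one value.**

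- Effect size at 42 per arm: (1.960 + 0.842) × √(2/42) = 0.61 (normal), or 0.62 (t).
- Completers at d = 0.58: 47 per arm (normal) or 48 (t; 47 gives 79.5% and 48 gives 80.3%). With 20% attrition, 94/0.8 = 117.5 and 96/0.8 = 120, so 118 to 120 randomized.

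**4. What a baseline covariate would recover.** If d = 0.58 is on the unadjusted scale, adjustment replaces d by d/√(1 − r²), where r is the correlation between baseline and end of treatment. The plan gives no r, so these are assumed values (t, 81 degrees of freedom): r = 0.30 gives 78.6%, r = 0.35 gives 80.1%, r = 0.50 gives 85.8%. The break-even is r = 0.348 (t) or 0.316 (normal).

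The pilot craving figure in section C is captioned "Cannabis craving by group and visit adjusted for baseline", so the 0.58 may already be a baseline-adjusted effect. In that case the covariate adds nothing to the calculation and power stays near 75%.

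**5. Use days.** The plan also says "The sample size of 42 completers per group will provide 80% power with a type 1 error rate of 5% to detect an 18% decrease"; the outcome there is self-reported use days, 39% against 57%. It gives no standard deviation. With one value per person, 80% requires a between-person SD of 0.18/0.619 = 0.29 (t). Over an assumed range, an SD of 0.25 gives 90%, 0.31 gives 75% and 0.35 gives 64%. The claim can be neither confirmed nor refuted. It is a reporting gap and not part of the error shown above.

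**The case against.** Nobody needs to dispute the arithmetic to resist the point. The case on the other side is this.

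- **The plan may not intend one unadjusted value.** The aim sentence refers to baseline and to both later time points, cannabinoid levels are collected at every visit, and associated covariates may enter the model. A modest baseline correlation would close the gap. This stands as a possibility. But the modelling sentence and the power text both name end of treatment, and the covariate rule depends on a significance screen and does not name baseline CN-THCCOOH. The power text uses no baseline correlation. If a two-visit or adjusted model is intended, the passages conflict and still need reconciling.
- **The two-visit factor is inferred.** True, but of the designs tried it is the only one that returns 84. A one-sided test of a single value would give about 84% power, but one-sided testing does not reproduce Aim 1's number.
- **More than 42 per arm may supply data.** With all 53, power would be about 84% (t) or 85% (normal). The statement is nevertheless tied to 42 completers.
- **The shortfall is small and the trial is a pilot.** This stands. A move from d = 0.58 to 0.62 is slight beside the uncertainty of an effect carried over from craving in a pilot of 33. About one point of the apparent 80-to-75 gap is only the normal approximation against the t test. The larger trial is to be planned from the observed variance, so this misstatement does not enter that calculation directly. These facts limit the weight of the point, but they do not make 80% the right figure for the analysis described.

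**Conclusion.** The concern holds. For CN-THCCOOH as D5 describes it, 42 completers per arm give about 75% power for d = 0.58, not 80%. The loss is 4.3 points on either method, and the effect detectable with 80% power is 0.61 to 0.62. This rests on a two-sided 5% test, one unadjusted end-of-treatment value per person, 42 completers per arm, and the inference that Aim 1's 84 came from a two-visit mean. The correction is worth making because the sample size is declared adequate on the strength of this figure, but the gap is modest and does not call for a larger trial.

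**What to change.** Either of two changes would do.

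1. **Restate the power.** For example: *42 completers per arm give about 75% power to detect d = 0.58 in end-of-treatment CN-THCCOOH, and 80% power to detect d = 0.62.*
2. **Prespecify baseline CN-THCCOOH as a covariate in the Aim 2 model**, independent of any significance screen. State the assumed correlation between baseline and end of treatment, and say whether d = 0.58 is an unadjusted or a baseline-adjusted effect. On the unadjusted scale, r of about 0.35 supports the 80% claim; on the adjusted scale, power remains near 75%.

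With either change, align the aim sentence with the modelling sentence so that the role of follow-up in Aim 2 is clear. For use days, add the SD and the test behind the 80%, and give the power for one value per person.

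The cost is one reworded paragraph or one added sentence in the model. No patients are added. The stated power becomes slightly less favourable unless the covariate route is taken and its correlation can be supported.

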1. RISKS TO THE SUBJECTS

a). Human Subjects Involvement and Characteristics

1. **Involvement of Humans:** Admission into the study is open to men and women and to all racial and ethnic groups, age 18-65. One-hundred and six subjects will be recruited primarily through internet and newspaper advertisements. Inclusion/exclusion criteria that apply to all subjects are listed below:

Inclusion criteria:

1. Be age 18-65 and must be able to provide informed consent.
2. Meet DSM-5 criteria for current moderate to severe CUD (past 60 days).
3. Identify cannabis as their primary substance of choice.
4. Express an interest in reducing marijuana use.
5. Consent to remain abstinent from alcohol and cannabis for 12 hours immediately prior to study visits and other drugs of abuse (except nicotine) for three days prior (see Additional Instrumentation below for methods); by restricting cannabis and other substance use as proposed, participants should not be under the acute effects of cannabis or other substances.

Exclusion Criteria:

1. Evidence of, or a history of serious medical or neurological disease that may affect cognitive processing.
2. History of, or current psychotic disorder, bipolar disorder, or current untreated major depressive disorder or attention-deficit hyperactivity disorder (ADHD) as these may interfere with subjective measurements.
3. Current use of psychotropic medications because these may affect subjective measurements (individuals taking antidepressants, or psychostimulants for ADHD will be allowed).
4. Current suicidal ideation. Individuals who endorse suicidal ideation will be seen by a psychologist or psychiatrist in the office and will be referred to treatment as necessary.
5. Women who are pregnant, nursing or of childbearing potential and not practicing an effective means of birth control.
6. Moderate to severe DSM-5 substance use disorder within the past 60 days (other than nicotine or cannabis).

2. Sample characteristics: We will recruit 106 adults age 18-65. We aim to recruit participants to approximate the cannabis treatment-seeking, racial, and ethnic composition of Charleston County, with the exception of gender, as we plan to enroll an equal number of males and females to address exploratory gender analyses (see Planned Enrollment Table).

b. Sources of Materials

1. **Research material to be obtained:** Structured diagnostic, psychosocial, substance use, and other cognitive questionnaires; behavioral tasks (i.e. MAAT computer task, cue-reactivity); breath and urine samples to detect recent substance use and pregnancy (in females); will be collected from participants. Every effort will be made to maintain participant confidentiality, in accordance with HIPAA.
2. **Data that will be recorded:** All forms of data described above will be recorded on computers or paper and pencil data forms that do not contain identifying information. Urine sample collection for toxicology analysis will be disposed by the federally certified lab; all samples will be code linked.
3. **Linkages to subjects and access to identities:** No personally identifying information will be recorded on the questionnaires, interviews, drug screen samples, behavioral data, or other scoring sheets assuring confidentiality. To ensure confidentiality, all subject data will be letter/number coded, and only the PI and HIPAA-trained research staff have access to the master code lists. All data will be stored in locked file cabinets in locked offices and on password-protected servers located behind secure and maintained firewalls.
4. **How data are collected and whether data will be collected specifically for proposed research:** Data are collected by the PI of the grant, co-investigators, or trained research associates. All staff will be required to complete on-line training in human subjects research, HIPAA, and clinical practices, PI-led in-lab training on research data management and confidentiality, and training to criterion on project protocol. Staff will also receive extensive training from [name] on how to handle any adverse events. Data will be collected specifically for this proposed research project.

c. Potential Risks

1. **Potential risks, likelihood, and seriousness:** Questionnaires and interviews are non-invasive and therefore involve minimal risk to participants.
 - a. **Craving or discomfort:** Exposure to cannabis cues may produce some craving for cannabis or other discomfort. However, this discomfort is usually brief and subjects will be in the cannabis-free safety of the human laboratory environment. In addition, exposure to cues will occur prior to psychosocial therapy sessions so any discomfort will be discussed by study therapists.
 - b. **Loss of confidentiality:** Confidentiality issues are significant since this study collects a variety of sensitive data, in particular with respect to substance use. Procedures described above minimize the possible breach of confidentiality. Since personal information is gathered, there exists the risk of possible invasion of privacy. However, since informed consent is obtained, the likelihood of invasion of privacy is minimal. A Certificate of Confidentiality will be obtained prior to study initiation.
2. **Alternative treatments and procedures:** Subjects who wish to seek alternative treatment will be given referral resources. Subjects will be informed that their participation is voluntary, which includes study discontinuation to seek treatment. Subjects who discontinue cannabis use during the course of the study will be allowed to complete the protocol.
3. **eSense Skin Response System (Mindfield Biofeedback)® GSR:** Though minimal, there is an inherent risk due to design and manufacturing such that defects or improper use may lead to electrical shock and catastrophic overheating could lead to burns.

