Remote screening visit: Patients may also complete the initial visit remotely if warranted. In this case, participants will be electronically consented using Doxy.me or REDCap. The informed consent will be emailed to the participant prior to the video call. The participant will have the opportunity to ask questions on the call and will electronically sign the document. A signed copy will be emailed to the participant. The M.I.N.I. interview will then be conducted, also via Doxy.me. Participants will be advised to find a private location during these procedures to protect privacy and confidentiality. Participants will be sent survey links to complete self-report questionnaires. Females will have a pregnancy test completed at Study visit 1.

D4.b. Session preparation: Participants will present to the Addiction Sciences Division research clinic for all study visits. The participant will be breathalyzed and will provide a urine sample which will be tested for pregnancy (females). If the pregnancy test is negative or the subject is male, the sample will be tested for the presence of cocaine, opiates, benzodiazepines, THC, and stimulants. A saliva sample will also be collected to verify cannabis abstinence for 12 hours prior to study procedures. If test results are within study inclusion/exclusion criteria, study visit procedures will begin.

D4.c. Approach Bias Modification (ABM): ABM procedures will use a cannabis adaptation of the Approach Avoidance Task²⁸ designed to assess and modify cannabis approach bias. Approach bias assessments: During the assessment phase, participants are presented with marijuana (MJ)-related and neutral images on a computer screen and are asked to push or pull a Logitech Extreme 3D Precision joystick in response to an irrelevant stimulus feature (i.e. image border color). Joystick movement activates a zooming feature, which has been shown to effectively model approach (pull: zoom in) and avoidance (push: zoom out) behavior²⁹. Participants are asked to respond to stimuli as quickly and accurately as possible and reaction times (RTs) are calculated from image onset to action completion (zoom off-screen). Approach bias is computed by subtracting median “approach MJ” RTs from median “avoid MJ” RTs ($RT_{\text{avoid}} - RT_{\text{approach}}$); a positive value thus indicates greater approach bias. Assessments will occur at three time points: Baseline (BL), End of Treatment (EOT), and Follow-Up (FU). Each assessment

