D4.e. Cue Reactivity: Cue reactivity will consist of physiological (skin conductance) and subjective (self-reported craving) components and will be assessed at three time points: BL, EOT, and FU. Participants will be connected to a finger sensor and then exposed to a neutral cue set, followed by a cannabis cue set. Each cue set contains tactile, auditory, and olfactory cues. Cannabis craving will be assessed prior to neutral cues, after neutral cues, and after cannabis cues to account for any carryover effects³³. Skin conductance will be assessed continuously with time markers of cue onset/offset noted by study personnel to be used for subsequent analysis. Cue reactivity will be assessed following approach bias assessments.

D4.f. Additional instrumentation:

Descriptive assessment of cannabis use: Cannabis use in the 30 days prior to baseline will be assessed using urine drug screens and the Timeline Follow-Back (TLFB)³⁴. The TLFB is a calendar-based instrument used with specific probes to ascertain detailed information about amounts of substance use. Number of discrete cannabis using sessions per day and quantity (hits) used per day will be recorded.

If necessary to limit person-to-person exposure, certain items such as the HAM-A, HAM-D and questions about substance use may be completed remotely. Participants may also be sent survey links to complete questionnaires remotely throughout study participation.

Menstrual History Diary: Subjects will be asked to estimate the timing of their cycle for the 90-days prior to study entry and to track their cycle during study participation.

Substance-related instruments: **TLFB:** Described above. In addition to cannabis use, participants will be asked about daily alcohol use (standard drinks), as well as instances (yes/no) of other substance use. **Urine Drug Screening:** Drug screens will be performed using the One Step Multi-Drug Test Dip Card (Drugconfirm™), a lateral flow chromatographic immunoassay for the qualitative detection of drug or drug metabolite in the urine at the following cutoffs (ng/ml): cocaine (300), amphetamines (1000), methamphetamine (1000), THC (50), opiates (2000), and benzodiazepines (300). Samples will then be sent to MUSC laboratory for cannabinoid quantification

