Neuropsychological assessments: Cognitive functioning will be assessed at BL, EOT, and FU to examine whether cognitive functioning is improved following the intervention or whether changes in cognitive functioning mediate treatment effect. To obtain additional measures of implicit cognitive bias, a cannabis adaptation of the dot-probe task that has shown sensitivity across substances of abuse^{40,41} will be used to assess cannabis attentional bias and a cannabis adaptation of the Implicit Association Task¹⁴ will be used to assess cannabis memory bias. Multiple forms of executive function shown to be impacted by SUDs will be assessed and which include: inhibitory control (Go No-Go task⁴²), working memory – verbal (WAIS-IV Digit Span Subscale) and nonverbal (N-Back⁴³) tasks. The Symbol Digit Modalities Test (SDMT)⁵⁴ measures sustained attention, response speed, and visuomotor coordination. It involves filling in a blank space below a symbol with the appropriate symbol-paired number as quickly as possible for 90 seconds.

D4.g. Six-Month Follow-up: Participants will complete a six-month follow-up either in person or over the phone. They will complete a TLFB, CWS, HAM-A, HAM-D, and review DSM-5 CUD symptoms from the M.I.N.I. neuropsychiatric interview. Participants will also complete the MJPS, PSQI, SF36 self reports in the Survey Mode of Redcap. Participants who do not complete the visit in person will be given the option to complete the surveys though a RedCap Survey Link sent though MUSC email. Participants who complete the visit in person will provide a UDS.

D4.h. Participant compensation: Participants will be compensated for attendance using an escalating contingency management (CM) schedule, cash bonuses, and a chip pick to maximize retention. Participants will be paid \$40 for the screening visit (\$20 for the interview and \$20 for the questionnaires/UDS). Participants will receive a cash incentive starting at \$20 at week 1 and increasing by \$5 each week; any missed session will reset the cash incentive to \$20. Participants will receive cash bonuses for completing baseline/week 1 (\$25) and week 4 (\$50) Participants will be apid \$50 at the one-month follow-up visit , and \$20 at the 6-month follow-up visit if completed in person. Participants who come to their visit and produce a negative saliva drug screen will also draw from a bowl

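### Self-reported cannabis use at Week 4 and 1 month can be lost in people who stop attending, although the protocol already has a phone method that could collect it

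*Combined protocol and SAP*

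**What the plan says.** - **Analysis set (D5, General Analysis):** "All analyses will be performed on the intent-to-treat sample consisting of all randomized subjects".
- **Place of visits (D4.b):** "Participants will present to the Addiction Sciences Division research clinic for all study visits".
- **Remote collection (D4.f):** "If necessary to limit person-to-person exposure, certain items such as the HAM-A, HAM-D and questions about substance use may be completed remotely". The next sentence also permits survey links for questionnaires during participation. It does not say whether the TLFB, a calendar completed with specific probes, counts as one of these.
- **Month 6 (D4.g):** "Participants will complete a six-month follow-up either in person or over the phone". The TLFB is part of that contact.
- **Other treatment (E.1.c, item 2):** people who want it receive referral resources, and "Subjects will be informed that their participation is voluntary, which includes study discontinuation to seek treatment".
- **Aim 2 model (D5):** use is summarized once per person at the end of the four weeks, with abstinence at the 1-month follow-up as a secondary question. On missing data, D5 says only, under Aim 1, that mixed models cope well with it.

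No section says that self-reported use will be sought from someone who stops attending before month 6. The visit schedule has no entry for treatment obtained elsewhere.

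**The concern.** An all-randomized analysis needs outcomes from people who stop the intervention as well as from those who finish. Here the self-report arm of Aim 2 depends on attendance at the two visits that matter most, Week 4 (end of treatment, EOT) and 1 month (FU). Yet the same instrument can be done by phone at month 6.

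Attendance may well be related to current use. Under D4.b, visit procedures go ahead only if the day's test results are acceptable. Under D4.h, prize draws after screening require a negative saliva screen. If loss depends on use that was never recorded, a model fitted to what was recorded does not fully correct for it. With one end-of-treatment summary per person, earlier visits give limited help.

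At stake is how far the use-days comparison describes everyone randomized rather than those who stayed. The trial's estimates are also meant to help power the next study.

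**Working it through.** **1. The plan's own figures.** D5 states that "a sample size of 84 participants would be necessary to detect the noted treatment effect size with 80% power". Taking the mean of two post-baseline measures with correlation 0.8, d = 0.58, and two-sided 5% (sidedness is not stated), the variance factor is (1 + 0.8)/2 = 0.9 and

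n per arm = 2 × (1.96 + 0.84)² × 0.9 / 0.58² ≈ 42, that is 84 in total.

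With 20% attrition, 42/0.8 = 52.5, rounded up to 53 per arm and 106 in total. Both figures reproduce. Loss of 20% is already allowed for in the sample size, so at that level the issue is bias rather than power.

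**2. How many people.** Planned attrition: 106 × 0.20 ≈ 21. Pilot follow-up loss (section C: 33 of 49 completed through follow-up): 106 × 16/49 ≈ 35.

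**3. Size of the bias, same use assumed in stoppers.** D5 plans for 57% use days on sham and 39% on ABM with 42 completers per group. Treat 18 points as the difference among those observed. Let stoppers use on S% of days in either arm, with loss p_s on sham and p_a on ABM. Then

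all-randomized difference = [(1 − p_s) × 57 + p_s × S] − [(1 − p_a) × 39 + p_a × S].

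S is not in the documents; 80 is assumed, with 70 to 90 as the range. The unequal splits are also assumed.

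| Loss on ABM / sham | S = 80 | S = 70 | S = 90 |
|---|---|---|---|
| 20% / 20% | 61.6 − 47.2 = 14.4 | 14.4 | 14.4 |
| 33% / 33% | 64.6 − 52.5 = 12.1 | 12.1 | 12.1 |
| 25% / 15% | 60.45 − 49.25 = 11.2 | 12.2 | 10.2 |
| 15% / 25% | 62.75 − 45.15 = 17.6 | 16.6 | 18.6 |

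With equal loss the result is 18 × (1 − p) whatever S is, because the formula gives stoppers the same use in both arms.

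**4. Dropping that restriction.** With equal loss m, let g be the gap in use days between missing and observed people. The all-randomized difference is 18 − m × (g_ABM − g_sham). If the gaps differ between arms by −20 to +20 points (assumed):

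- m = 0.20: 18 ± 4, that is 14 to 22 points.
- m = 16/49: 18 ± 6.5, that is 11.5 to 24.5 points.

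The error can have either sign.

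**5. What calls could recover.** Suppose half of the stoppers are reached and resemble the rest (assumed), with S = 80.

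- Loss 20% / 20%: (45.6 + 8)/0.9 − (31.2 + 8)/0.9 = 59.6 − 43.6 = 16.0, against 14.4 for everyone. The error falls from 3.6 to 1.6 points.
- Loss 25% ABM / 15% sham: (48.45 + 6)/0.925 − (29.25 + 10)/0.875 = 58.9 − 44.9 = 14.0, against 11.2. The error falls from 6.8 to 2.8 points.

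**The case against.** The strongest reply is that the loss is inferred from silence. The sentence in E.1.c is a statement of voluntariness in the risk section. D4.h resets the cash incentive after a missed session, which presupposes that absentees come back. The TLFB is retrospective and scheduled at every visit, so use up to the last attended visit is on record, and a missed Week 4 might be filled in at 1 month. The consent form is not among the documents and may set terms for follow-up after withdrawal. All of this stands. It limits the claim to data that can be lost, not data that must be. It does not supply a rule for someone who stops coming, and neither the recall window after baseline nor the handling of a partial calendar is stated.

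Some stronger readings are tempting but not supported:

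- **That anyone who seeks other treatment is removed.** E.1.c describes the participant's own choice, and no text removes anyone.
- **That use can only be recorded in clinic until month 6.** D4.f allows remote substance-use questions earlier; the limit is the stated reason for using them.
- **That about 21 people will lack Week 4 data because 10 of 49 in the pilot did not complete all four sessions.** Missing any session is not the same as missing Week 4. The pilot also enrolled people not seeking treatment, and its losses were from all causes.
- **That 1-month use after outside treatment is uninterpretable.** An all-randomized comparison can include use whatever treatment followed.

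**Conclusion.** The point holds as a cheap improvement. Following the plan as written can lose self-reported use at EOT and 1 month in non-attenders, although the analysis claims everyone randomized and the protocol has a means of collecting it.

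If stoppers use on 80% of days, the planned 18 points corresponds to about 11 to 18 points in everyone randomized (11.2 to 17.6 in the cases above). This rests on assumed use in stoppers, assumed splits of loss, and an analysis that does not recover the missing values from other data.

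A reader might infer that the trial will overstate the effect. The documents do not support a direction. The shrinkage in the equal-loss cases comes from giving stoppers identical use in both arms, and reversing the unequal split gives 17.6 points, almost no bias. With gaps that differ by arm, the all-randomized difference can exceed 18.

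**What to change.** These changes concern data collection only and leave referral and clinical handling as they are.

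- **E.1.c, item 2:** state that stopping sessions or starting other treatment does not by itself end outcome follow-up, and that only withdrawal of consent does. Align the consent wording.
- **D4.b and D4.f:** allow the TLFB by phone or video at Week 4 and the 1-month visit for any consenting participant who does not attend, as D4.g does at month 6. State which days the call covers.
- **TLFB calendar:** note the date any other cannabis treatment started.
- **D5, Aim 2:** include these values in the use-days analysis.
- **Payment:** do not pay the full in-person amount for a call. D4.h pays the 6-month visit only when it is in person, and full payment could weaken attendance for outcomes that need a visit.

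**Cost:** a short amendment and some extra calls by existing staff: about 21 people at Week 4 if the planned 20% attrition falls there, and about 35 at 1 month if the pilot's follow-up loss recurs.

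**Downside:** phone reports have no urine confirmation. They serve use days only, not creatinine-corrected cannabinoid levels, urine-confirmed abstinence or cue reactivity. People who withdraw consent will still be missing.
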